 - f. Aspartate aminotransferase (AST) and alanine aminotransferase (ALT) $\leq 1.5 \times$ ULN
 - g. Alkaline phosphatase (ALP) $\leq 1.5 \times$ ULN
 - h. Estimated glomerular filtration rate (eGFR) $> 60 \text{ mL/min}$ as determined by the Chronic Kidney Disease Epidemiology Collaboration equation.
 - i. Negative serum pregnancy test for individuals of childbearing potential (IOCBP)
11. IOCBP, defined as assignment of female sex at birth, not surgically sterilized (hysterectomy, bilateral salpingectomy, and bilateral oophorectomy), and between menarche and 1-year post menopause, must have a negative serum pregnancy test performed within 72 hours prior to initiation of study drug. IOCBP must agree to abstain from egg donation during the course of the study.
12. IOCBP and male participants with partners of IOCBP must agree to use highly effective methods of contraception according to **Section 8.1.3** from the time of consent through 6 months after discontinuation of study drug. Male participants must agree to abstain from sperm donation during the course of the study.
13. IOCBP is not pregnant, expecting to become pregnant, or breastfeeding or male participant is not expecting to father children within the projected duration of the study, starting with screening visit through 6 months after the last dose of study drug.

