12.2 Adverse Event Collection and Documentation

12.2.1 Adverse Events

AEs and SAEs will be collected from the time the participant consents to study participation. AEs and SAEs reported between the time the participant signs the informed consent form and administration of the first dose of study drug will be captured as concurrent medical history unless the events are attributed to protocol-specified procedures.

Events attributed to protocol-specified procedures will be collected on the AE eCRFs and SAE Report Form, as appropriate.

AEs, regardless of seriousness, severity, or relationship to study drug(s), are documented in the source and the eCRF, including:

- Duration, severity, and seriousness of each AE.
- Action taken with respect to the study drug(s).
- Investigator's attribution/causality assessment.

- Any medications used to treat the AE.
- Outcome of the event.

A diagnosis should be recorded when signs and symptoms are due to a common etiology (e.g., cough, runny nose, sneezing, sore throat, and head congestion should be reported as "upper respiratory infection"). All treatment measures for AE management will be recorded. All non-serious AEs should be entered into the eCRFs within 10 days of study site awareness.

Clinical Laboratory Changes: Clinical laboratory test results are evaluated by the investigator for clinical significance. The investigator is responsible for reviewing the results of all laboratory tests in a timely manner. The investigator may repeat the laboratory test or request additional tests to verify the results of laboratory tests.

Clinically significant laboratory abnormalities are reported as AEs. A laboratory abnormality is considered clinically significant if it is associated with study drug discontinuation, study drug dose reduction or delay, requires an intervention, or it is suggestive of disease or organ toxicity.

Laboratory abnormalities associated with a diagnosed AE are not reported as separate AEs. For example, report renal failure or hematuria, not the laboratory abnormality (e.g., elevated creatinine or urine red blood cells increased).

The sponsor reports all suspected unexpected serious adverse reactions (SUSARs) to the regulatory authorities and the investigator. The investigator must report SUSARs to the IRB of record as required by the site's institutional policy.

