4.8.2 Laboratory Values and Analyses

Summaries of laboratory values will display descriptive statistics for numerically quantified labs. Summaries will be grouped by lab panel (e.g., hematology, blood chemistry, and urinalysis) and will be displayed by visit for each lab parameter.

In cases where an abnormality resulted in a repeat lab test, the repeat value will be used for the summaries. A list of repeated labs including original values and repeat values will be included.

Shift tables will be used to display the number and percent of participants who have a shift in their lab value normality between baseline and each post-baseline visit.

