4.8.3 Other Safety Endpoints and Analyses

Electrocardiograms (ECGs) will be collected and analyzed for evidence of cardiac toxicity, especially prolongation of QT interval. Summary statistics will be tabulated for ECGs parameters. The following categories for QTc interval and maximum post dose change from baseline QTc will be used in summary:

QTc: \leq 450 msec, > 450 to 480 msec, > 480 to 500 msec, and > 500 msec

Vital signs will be summarized with descriptive statistics at each visit and time point where they are collected. Shift tables may be produced to display percent of participants who have a shift from normal between baseline and each post-baseline visit.

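### Laboratory shift tables sort values only as normal or abnormal, so worsening from an already high baseline shows as no shift; add a baseline-to-worst-grade table

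*SAP*

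**What the plan says.** SAP 4.8.2 plans three laboratory outputs:

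- Descriptive statistics that "will be displayed by visit for each lab parameter". SAP 4.1 says continuous summaries include minimum and maximum.
- A listing of repeated tests with original and repeat values. For the tables themselves the rule is: "In cases where an abnormality resulted in a repeat lab test, the repeat value will be used for the summaries".
- Shift tables giving "the number and percent of participants who have a shift in their lab value normality between baseline and each post-baseline visit".

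None of the three uses a toxicity grade, a multiple of the upper limit of normal (ULN), or a worst post-baseline value. Protocol 14.7.2 makes shift tables optional and defines no categories.

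Protocol 5.1, item 10, admits AST, ALT and ALP up to 1.5 x ULN, total bilirubin below 1.5 x ULN (with a condition on direct bilirubin when the total is raised), and prothrombin time or INR up to 1.1 x ULN.

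Adverse events are graded on DAIDS v2.1 (Protocol 12.1.6) and tabulated by grade (SAP 4.8.1). Laboratory findings enter that route by this rule in Protocol 12.2.1: "Clinically significant laboratory abnormalities are reported as AEs".

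**The concern.** Safety is the primary objective, and the study's safety rules are written in grades. Protocol 4.3 places the DLT line at Grade 2, with a specific exception for short-lived Grade 2 laboratory abnormalities. The suspension rule in Protocol 14.9 turns on Grades 2 and 3. A laboratory display ought to let a reader see change on that scale, independently of whether the investigator reported an event.

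A shift table based on normality does not do this. Entry criteria allow participants to start above normal on several liver and coagulation tests, and for them further worsening produces no shift. For those who start normal, the table cannot separate a marginal crossing from a large rise. What is at stake is how completely the report describes laboratory changes that were not reported as adverse events.

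**Working it through.** The plan states no figure to reproduce. The check applies the normality rule to pairs of values.

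**Inputs.** The rule comes from SAP 4.8.2 and the entry ceiling of 1.5 x ULN for AST, ALT and ALP from Protocol 5.1. The value pairs are assumed for illustration; every abnormal baseline lies within the entry ceiling.

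**Rule.** Normal if the value is at most 1 x ULN, otherwise high. A shift is counted when the two categories differ.

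| Baseline (x ULN) | Follow-up (x ULN) | Ratio | Categories | Counted as |
|---|---|---|---|---|
| 1.40 | 1.45 | 1.45/1.40 = 1.04 | high to high | no shift |
| 1.40 | 2.80 | 2.80/1.40 = 2.0 | high to high | no shift |
| 1.40 | 8.40 | 8.40/1.40 = 6.0 | high to high | no shift |
| 0.98 | 1.02 | 1.02/0.98 = 1.04 | normal to high | shift |
| 0.90 | 8.40 | 8.40/0.90 = 9.3 | normal to high | shift |
| 1.02 | 0.98 | 0.98/1.02 = 0.96 | high to normal | shift |

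A stable high value, a doubling and a six-fold rise share one cell. A 4% rise across the limit and a nine-fold rise share another. A low/normal/high layout changes nothing here, because high to high stays on the diagonal.

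**Effect on a displayed rate.** One participant classified one way or the other moves the shift rate by 1/3 = 33 percentage points in a cohort of three and 1/6 = 17 points in a cohort of six.

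**Other planned outputs.**

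- By-visit minimum and maximum. In a cohort of one or three, an extreme value at a tabulated visit would be visible if summaries are shown by cohort. The statistic does not show that participant's baseline. Tests are run locally (Protocol 9.11.1) at 3-5 institutions (Protocol synopsis), so raw maxima may not share one ULN.
- Adverse event tables by grade. These capture the change only when it meets the clinical-significance rule. The 8.40 x ULN rows would very likely qualify, since Protocol 12.2.1 includes findings that suggest organ toxicity. A doubling from 1.40 to 2.80 is more open to judgement.
- Listing of repeats. It keeps the original value, but the tables use the repeat, so a transient abnormality can drop out of the shift count.

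**Off-schedule values.** Protocol Tables 7 and 8 allow additional safety tests. As Table 8 reads, Part 2 chemistry is scheduled on Day 29 (last dose) and next on Day 78, a gap of 78 - 29 = 49 days, while the DLT period runs two weeks past the last infusion (Protocol 4.3). A chemistry result obtained in between would be off-schedule, and SAP 4.8.2 does not say where it goes.

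**The case against.** The strongest reply is that the shift table is one display among several and carries no decision. The primary endpoint is the incidence of treatment-emergent and serious adverse events and of those leading to discontinuation (Protocol 3.1). A DLT is a graded, treatment-related adverse event. Escalation rests on direct review of laboratory parameters and other safety data (Protocol 4.2 and 14.9). Cohorts are small enough to review participant by participant. SAP section 5 leaves table shells and programming specifications to a separate Statistical Programming Plan, which may hold finer categories.

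Most of this stands, and it rules out several stronger readings that a reader might infer:

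- That the report cannot show a Grade 2 or worse laboratory change. It can, through the adverse event tables, and a by-visit maximum may point to one.
- That a participant with an abnormal baseline can never register a shift. A return to normal is a shift; only worsening in the same direction is lost. Entry limits also apply at screening, and a Day 1 sample may be the baseline.
- That unscheduled samples are excluded. The SAP refers to post-baseline visits without saying scheduled; it is silent, not exclusionary.
- That dose decisions could be misled. No rule in either document uses the shift table.

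The reply does not remove the core. SAP 4.8.2 itself fixes the shift category as normality, so this is a stated choice and not only missing shell detail. Individual review is feasible, but the SAP plans no listing of graded laboratory worsening to support it. Protocol 12.1.1 does count abnormal test results in its general definition of an adverse event, yet the operative reporting rule in 12.2.1 is clinical significance.

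**Conclusion.** The point holds as a limited reporting weakness. In the planned shift tables, worsening from an already high baseline is shown as no shift, and marginal and large crossings are indistinguishable. The gap that remains after the other outputs are counted is moderate worsening that the investigator did not judge clinically significant. Such a change would appear, if at all, only as an unlinked by-visit statistic.

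The size in this trial cannot be estimated. The documents give no frequency of abnormal baselines, and the DAIDS laboratory thresholds are not reproduced in them, so it cannot be said here which illustrative values would reach Grade 2. The 33 and 17 point figures show only what one participant is worth. The conclusion assumes that normality means position relative to the reference range and that the Statistical Programming Plan, which is not available, does not add graded categories. The change is worth making because it is cheap and serves the primary objective; the safety rules do not depend on it.

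**What to change.** Keep the by-visit summaries, which preserve the time course. Add to SAP 4.8.2:

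- A shift table of baseline DAIDS v2.1 grade against worst post-baseline grade through end of study, by part and dose level, for parameters that the scale grades, with low and high directions separated where relevant.
- A statement that this table uses unscheduled values and the original values before any repeat.
- A listing of each participant who reaches Grade 2 or higher with an increase from baseline grade.

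The data are already collected and the study already uses this scale, so no new sampling is needed. Protocol 14.7.2 leaves shift tables open, so a SAP edit is enough. The cost is a grade derivation that must use each site's local reference ranges, plus one extra table and one listing.

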4.8.3 Other Safety Endpoints and Analyses

Electrocardiograms (ECGs) will be collected and analyzed for evidence of cardiac toxicity, especially prolongation of QT interval. Summary statistics will be tabulated for ECGs parameters. The following categories for QTc interval and maximum post dose change from baseline QTc will be used in summary:

QTc: \leq 450 msec, > 450 to 480 msec, > 480 to 500 msec, and > 500 msec

Vital signs will be summarized with descriptive statistics at each visit and time point where they are collected. Shift tables may be produced to display percent of participants who have a shift from normal between baseline and each post-baseline visit.

4.9 Exploratory Endpoints and Analyses

The endpoints described in Sections 4.12.2-4.12.7 below are exploratory and only include participants from one or multiple parts of the study. The described analyses of these endpoints are optional and may not be performed if sample size does not permit.

4.10 Pharmacokinetic Endpoints and Analyses

Summary statistics will be tabulated for PK parameters by dose. Geometric means and percent coefficients of variation may be reported for maximum concentration (C_{max}), lowest concentration (C_{min}) observed at the last study point, area under the curve (AUC) for Parts 1A and 1B, area under the curve for 2 week interval (AUC_{tau}) for Part 2, and trough concentration (C_{trough}) for Part 2; arithmetic means and standard deviations (SD) may be reported for terminal half-life ($t_{1/2}$), clearance (CL), and steady-state volume of distribution (V_{ss}); and medians, minimum, and maximum will be reported for time to maximal concentration (T_{max}).

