2.3.2.1 MGD014 Clinical Experience

One clinical study of MGD014, Study CP-MGD014-01, is complete. This trial was a Phase 1, open-label, single-center study to evaluate the safety, immunologic, and virologic responses of MGD014. Refer to the **MGD014 IB** for additional information.

As of 26 September 2020, Study CP-MGD014-01 enrolled 21 PWH on ART and dosed with single-dose MGD014 as follows: 1 participant each at 0.1 and 0.3 mcg/kg; 4 participants at 1 mcg/kg; and 3 participants each at 3, 10, 30, 100, and 300 mcg/kg MGD014.

Treatment-related AEs were reported among 4 of 21 (19.0%) participants receiving MGD014. These included AEs of feeling hot (n = 1 at 3.0 mcg/kg), diarrhea (n = 1 at 10 mcg/kg), flushing (n = 1 at 100 mcg/kg), and electrocardiogram QT prolonged and sensory disturbance (both in the same participant at 100 mcg/kg). All AEs were Grade 1 in severity, possibly related to MGD014, and occurred on the day of study drug infusion. All treatment-related AEs resolved without intervention. No dose-limiting toxicity (DLT), serious adverse events (SAEs), deaths, or treatment-related AEs leading to study drug discontinuation were reported.

Eighteen participants were evaluable for preliminary PK analysis following single administration of 0.1, 0.3, 1, 3, 10, 30, or 100 mcg/kg of MGD014. Dose normalized values of C_{max} and area under the concentration-time curve from time zero to infinity (AUC_{0-inf}) are approximately constant for the 3 to 100 mcg/kg doses, indicating dose proportionality in MGD014 PK for this dose range. Estimates for $t_{1/2}$, volume of distribution in liters, and CL of MGD014 are 10-12.5 days, 11-22 L, and 0.04 L/hr, respectively.

There were no increases in serum cytokine (IFN- γ , TNF- α , interleukin [IL]-2, IL-5, IL-6, or IL-10) concentrations or increases in activation markers (CD25, CD69, CD134, or CD137) on circulating CD4 $^{+}$ or CD8 $^{+}$ T cells following MGD014 administration. Most circulating CD4 $^{+}$ or CD8 $^{+}$ T cells exhibited MGD014 binding at 24 hours following MGD014 administration at 100 or 300 mcg/kg.

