2.4 Dose Selection

2.4.1 MGD020 Dose Selection

A first-in-human starting dose of 1 mcg/kg MGD020 is proposed. Rationale supporting this dose selection is based on nonclinical data with MGD020 and nonclinical and clinical data with MGD014. MGD014 is a DART molecule with a structure like MGD020 but with specificity for a different HIV-1 env epitope. The MGD020 MABEL of 7 ng/mL corresponds to the median EC₅₀ for in vitro redirected T-cell cytotoxicity of human CD4⁺ cells infected by HIV-1 IMCs. An MGD020 starting dose of 1 mcg/kg is projected to yield a C_{max} of ~24 ng/mL, which exceeds the MABEL by ~3-fold. The 1 mcg/kg dose is expected to be a safe starting dose for MGD020 based on the rarity of target cells (HIV-1-infected, env-expressing cells) in PWH on ART, and thus the risk of adverse effects due to cytokine release or T-cell activation resulting from MGD020-mediated activity is minimal. The starting dose is supported by a study conducted in SHIV-infected rhesus monkeys on ART in which MGD020 was well tolerated when administered at 1 mg/kg weekly for 6 weeks. The 1 mg/kg dose yielded mean C_{max} of 27,200 ng/mL with no increases in serum cytokines or activation of circulating T cells. The starting dose is also supported by clinical experience with MGD014. MGD014 was well tolerated in Study CP-MGD014-01 conducted in PWH on ART when administered at doses ranging from 0.1 to 300 mcg/kg with mean C_{max} of 23.7 ng/mL at 1 mcg/kg and 5108 ng/mL at 300 mcg/kg. No DLT or SAEs were observed. There were no increases in serum cytokines or activation of circulating T cells following MGD014 administration at all dose levels examined.

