4.1.3 Part 2: Multi-Dose Expansion Cohort: Fixed-Dose of MGD020 and Fixed-Dose of MGD014

Part 2 commences only after an MTD or MAD of MGD020 in combination with MGD014 has been determined in Part 1B. Part 2 is a multi-dose expansion cohort with sequential infusions of a fixed dose of MGD020 in combination with a fixed dose of MGD014 administered Q2W for 3 combination doses over 4 weeks (**Table 3**). MGD020 is dosed at the MTD/MAD determined in Part 1B (i.e., MTD_{1B}/MAD_{1B}). MGD014 is dosed at 300 mcg/kg, as determined from Study CP-MGD014-01.

Up to 6 participants may be enrolled in Part 2 using a conventional 3+3 design. If 2 or more participants in the cohort of 6 participants experience a DLT, enrollment and further dosing of ongoing participants will be suspended pending further assessment of safety data.

Table 3 MGD020 and MGD014 Combination Multi-Dose Expansion Cohort Scheme (Part 2)

Cohort	MGD020 ^a (mcg/kg)	MGD014 (mcg/kg)	Design
1	MGD020 MTD _{1B} /MAD _{1B}	300	3+3

- a The MGD020 dose is determined by the combination MTD or MAD in Part 1B.

Participants who completed Part 1 may be considered for enrollment in Part 2, provided they meet all eligibility criteria, did not experience DLT in Part 1, and do not have detectable ADA against MGD014 and/or MGD020 at the completion of Part 1.

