6.4 Study Drugs and Supplies

6.4.1 MGD020

The concentration and function of each component in the DP are summarized in **Table 4**.

MGD020 is supplied as a sterile aqueous solution packaged in a United States Pharmacopeia (USP) and European Pharmacopoeia (Ph. Eur.) conforming Type I borosilicate, 10 cc clear flint glass vial with a 20 mm West 4023/50 gray butyl rubber serum stopper with B2-40® and FluroTec® coating on the plug. The vial is sealed with a 20 mm TruEdge® aluminum closure with a plastic overseal.

MGD020 will generally be administered over 60 minutes by IV infusion after dilution in Infusion may be slowed for IRR (see **Section 7.1**) but should be completed within 120 minutes. MGD020 must not be administered as an IV push or bolus.

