10 ASSESSMENT OF PHARMACOKINETICS AND PHARMACODYNAMICS

10.1 Pharmacokinetic Assessments

Serum concentrations of study drug(s) will be assessed using quantitative validated bioanalytical methods. Single-dose and multiple-dose PK parameters will be derived from serum concentration versus time data. These parameters may include maximum concentration (C_{max}), time to maximal concentration (T_{max}), area under the concentration-time curve for a dosing interval (AUC_{tau}), trough concentration (C_{trough}), clearance (CL), volume at steady state (V_{ss}), and terminal half-life ($t_{1/2}$).

Analysis of PK data will be performed using industry standard software. Population PK analyses may be conducted using data from this study alone or combined with data from other sponsor-conducted studies.

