b For participants who have been previously exposed to MGD014 or MGD020, obtain screening samples for ADA (MGD014 and MGD020) at least 21 days prior to enrollment to allow for results to be reported before enrollment.

c PK, ADA and cytokine samples may be obtained selectively at additional time points in participants who experience signs and symptoms of IRR or CRS.

Abbreviations: ADA: anti-drug antibody; CRS: cytokine release syndrome; EOI: end of infusion; EOS: end of study; HLA: human leukocyte antigen; IPDA: intact proviral DNA assay; IRR: infusion related reaction; N/A: not applicable; PBMC: peripheral blood mononuclear cell; PD: pharmacodynamic; PK: pharmacokinetic.

Table 11 Pharmacokinetic, Immunogenicity, and Pharmacodynamic Sampling Schedule: Part 2

Study Day	Time Point	Window	PK ^a (Serum)		ADA (Serum)		Cytokines (Serum)	PD: T-cell Binding & Phenotype (Whole Blood)	PD: IPDA & rca- RNA (PBMCs)	HLA Typing (Whole Blood)	PD: QVOA (Leuka- pheresis)	PD: SCA (Plasma)
			MGD020	MGD014	MGD020	MGD014						
-56 to -1	Screening	N/A			X ^b	X ^b					X ^c	
1	Pre-MGD020 infusion	N/A	X	X			X	X	X	X		X
1	EOI MGD020	+ 10 min	X									
1	EOI MGD014	+ 10 min		X								
1	1 h after EOI MGD014	± 5 min	X	X			X	X				
1	4 h after EOI MGD014	± 5 min	X	X			X	X				
2	No specific time	N/A	X	X			X	X				
4	No specific time	N/A	X	X								
8	No specific time	± 1 day	X	X			X	X				
15	Pre-MGD020 infusion	N/A	X	X	X	X	X	X				
15	EOI MGD020	+ 10 min	X									
15	EOI MGD014	+ 10 min		X								
15	4 h after EOI MGD014	± 5 min	X	X			X	X				
29	Pre-MGD020 infusion	N/A	X	X	X	X	X	X				
29	EOI MGD020	+ 10 min	X									
29	EOI MGD014	+ 10 min		X								
29	4 h after EOI MGD014	± 5 min	X	X			X	X				
43	No specific time	± 2 days	X	X					X		X ^c	X
50	No specific time	± 2 days	X	X								
64	No specific time	± 3 days	X	X								
IRR-CRS ^d	No specific time ^d	N/A	X	X	X	X	X					
78/EOS	EOS	± 3 days	X	X	X	X						X

a Obtain pre-infusion PK samples before start of infusion on visit day (dosing day) or day before. When collecting multiple samples, collect PK sample first.

b For participants who have been previously exposed to MGD014 or MGD020, obtain screening samples for ADA (MGD014 and MGD020) at least 21 days prior to enrollment to allow for results to be reported before enrollment.

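### Part 2 has no scheduled PK sample between 4 h and 14 days after doses 2 and 3, so a non-compartmental AUCtau from either interval would be biased upward; SAP 4.10 should limit it to dose 1

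*SAP*

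**What the plan says.** In Part 2 both drugs are "administered Q2W for 3 combination doses over 4 weeks", that is, on Days 1, 15 and 29. PK of each drug is a secondary objective, and Part 2 is the only part with repeated dosing.

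Protocol 10.1 commits to both kinds of parameter: "Single-dose and multiple-dose PK parameters will be derived from serum concentration versus time data". SAP 4.10 lists what may be reported, including "area under the curve for 2 week interval (AUC_{tau}) for Part 2". It also lists CL, Vss and half-life, without tying these to any part. Neither document names the dose after which AUCtau is taken, or a linear or logarithmic trapezoidal rule. Population PK is optional in Protocol 10.1 and 14.5.1 and is not mentioned in SAP 4.10.

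Part 2 PK times in Protocol Appendix 2, Table 11:

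- **Dose 1:** pre-dose, end of infusion, 1 h, 4 h, Days 2, 4 and 8, and Day 15 pre-dose.
- **Dose 2:** pre-dose, end of infusion, "4 h after EOI MGD014", then Day 29 pre-dose.
- **Dose 3:** pre-dose, end of infusion, 4 h, then Day 43, followed by Days 50, 64 and 78.

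Only event-driven samples for an infusion reaction or cytokine release could fall inside the gap.

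**The concern.** A trapezoid from 4 h to 14 days joins a near-peak value to a trough. If concentrations fall steeply over the first days and slowly afterwards, the true curve lies well below the line joining those two points, and the computed area is too large. The error has the same direction in every participant, so averaging over at most 6 people does not remove it.

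Dose 1 is sampled well enough to avoid the problem. Setting a dose 3 AUCtau beside a dose 1 AUCtau would therefore mix a biased value with a nearly unbiased one. It could suggest accumulation and a fall in clearance that the drugs do not show. The biased values could also enter the exploratory plots of PD change against exposure (Protocol 14.5.3, SAP 4.12).

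**Working it through.** The documents give no AUCtau figure to reproduce, so the check builds a concentration curve from their MGD014 figures and applies the Table 11 times to it.

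**Inputs from the documents**
- Terminal half-life, volume and clearance (Protocol 2.3.2.1): "volume of distribution in liters, and CL of MGD014 are 10-12.5 days, 11-22 L, and 0.04 L/hr, respectively"; the first figure is the half-life.
- Mean Cmax (Protocol 2.4.1): "5108 ng/mL at 300 mcg/kg".
- Infusion time (Protocol 6.4.1): "MGD020 will generally be administered over 60 minutes by IV infusion"; MGD014 is the same.
- MGD020 PK is expected to be comparable to MGD014 (Protocol 2.4.1.1).

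**Assumptions not in the documents:** body weight 60-90 kg; distribution half-life 0.25-3 days.

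**Step 1: are the inputs coherent?** t½ = ln2 × V/CL. With V 11-22 L and CL 0.04 L/h this gives 7.9-15.9 days, which brackets the stated 10-12.5 days.

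**Step 2: is there a distribution phase?** Initial volume ≈ dose/Cmax = 300/5.108 = 59 mL/kg, or 4.1 L at 70 kg, against a stated 11-22 L. A single exponential does not fit both figures.

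**Step 3: one case worked by hand.** Take 70 kg, CL 0.04 L/h = 0.96 L/day, terminal half-life 10 days and distribution half-life 1 day, with the dose treated as a bolus.
- Dose = 0.3 × 70 = 21 mg; AUC to infinity = 21/0.96 = 21.9 mg·day/L.
- α = 0.693/day, β = 0.0693/day. Solving A + B = 5.108 and A/α + B/β = 21.9 gives A = 3.99, B = 1.12 mg/L.
- After dose 3 the slow term carries over by 1 + 0.379 + 0.144 = 1.52, so C(t) = 3.99e^(−0.693t) + 1.70e^(−0.0693t).
- C(4 h) = 5.24; C(14 d) = 0.645.
- True AUCtau = 5.76 + 15.24 = 21.0.
- Area from 0 to 4 h = 0.91. Linear rule for the remaining 13.83 days: 13.83 × (5.24 + 0.645)/2 = 40.7. Total 41.6; ratio 1.98.
- Log rule: 13.83 × (5.24 − 0.645)/ln(5.24/0.645) = 30.3. Total 31.2; ratio 1.49.
- With the 1-h infusion carried through, the totals are 41.2 and 31.1, and the ratios 1.96 and 1.48.
- Dose 1 on its own Table 11 times: true 15.8, linear 16.7 (1.06), log-down 16.2 (1.03).
- Dose 3/dose 1 would read 41.2/16.7 = 2.5 (linear) or 31.1/16.2 = 1.9 (log-down), against a true 21.0/15.8 = 1.3.

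**Step 4: the range.** There were 140 admissible two-compartment curves, with terminal half-life 10 or 12.5 days, scaled either to CL 0.04 L/h or to V 11 or 22 L. Computed AUCtau divided by true AUCtau, with medians in brackets:

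| Interval | Linear | Linear-up/log-down |
|---|---|---|
| Dose 1 | 1.02-1.08 (1.05) | 1.00-1.04 (1.02) |
| Dose 2 | 1.21-2.60 (1.70) | 1.05-1.86 (1.34) |
| Dose 3 | 1.19-2.49 (1.66) | 1.06-1.81 (1.31) |

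If dose 3 also had samples at 1, 3 and 7 days, the ratio would fall to 1.01-1.07 (linear) or 1.01-1.03 (log-down). The sampling gap is therefore the cause. In a one-compartment limit the dose 2-3 ratios would be only 1.05-1.07 and 1.00, but Step 2 argues against that shape.

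**Step 5: direction for CL and Vss.** CL = Dose/AUCtau, so an inflated AUCtau lowers it. For dose 3, CL is 0.40-0.84 of the value from the exact AUCtau (linear) or 0.55-0.95 (log-down). With Vss = CL × MRT and MRT = (AUMCtau + τ × AUC from τ to infinity)/AUCtau, Vss is 0.15-0.63 or 0.39-0.95 of true. The third interval reaches only about 90-95% of steady-state exposure, which pushes CL up by 6-11% and offsets the bias only in part.

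**The case against.** The strongest reply is that nothing in the plan commits anyone to the faulty calculation. SAP 4.10 says only that AUCtau may be reported, and neither document prescribes a trapezoid or names dose 2 or 3. Dose 1 spans exactly one 14-day interval and is well sampled, so the schedule fits a design with AUCtau from dose 1 and peaks and troughs afterwards. The multiple-dose parameters of Protocol 10.1 could be just Cmax, Ctrough and terminal half-life. Population PK is already permitted. All of this stands, and it makes the point conditional. It does not remove it: the plan does not confine AUCtau to dose 1, and it does not assign doses 2-3 to a model.

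A reader might infer four stronger things that the documents do not support:

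- **That CL and Vss would be overstated along with AUCtau.** The arithmetic runs the other way.
- **That the SAP plans CL and Vss from Part 2.** SAP 4.10 gives them no part label. They can come from Part 1A/1B, where sampling runs to Day 43.
- **That an accumulation ratio or a dose 3 versus dose 1 clearance comparison is planned.** Neither document plans one.
- **That the cytokine exposure-response work depends on AUCtau.** It is framed on serum concentrations and is optional.

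The size is also uncertain. It rests on assumed weights and distribution half-lives. It also combines a Cmax at 300 mcg/kg with preliminary estimates of half-life, volume and CL from doses of 0.1-100 mcg/kg.

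**Conclusion.** The point holds in conditional form. If a non-compartmental AUCtau is computed after dose 2 or 3 of Part 2, it will be too high in every two-compartment case examined: roughly 1.05- to 1.9-fold by linear-up/log-down and 1.2- to 2.6-fold by the linear rule. Any CL or Vss taken from it will be too low. The direction follows from the sampling gap together with the stated Cmax and volume. The size depends on the assumed weight (60-90 kg) and distribution half-life (0.25-3 days), and on MGD020 behaving like MGD014.

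The dose 1 AUCtau, observed peaks and troughs, terminal half-life and Part 1A/1B parameters are sound. The primary safety objective is untouched. The gap does bear on a secondary objective in the only multiple-dose part, so the SAP should close it.

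**What to change.** In SAP 4.10:

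- State that non-compartmental AUCtau in Part 2 is computed for the dose 1 interval only (Days 1-15), and name the trapezoidal rule.
- State that any AUCtau, CL, Vss or accumulation estimate for doses 2-3 comes from a compartmental or population PK model fitted to all Part 1 and Part 2 concentrations.
- Keep observed Cmax, Ctrough (Days 15, 29 and 43) and terminal half-life (Days 43-78) as they are.

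The cost is a few sentences and modest modelling work of a kind the protocol already permits, with no new visits or samples. A model fitted to few participants brings its own assumptions, which should be reported with the estimates. If a non-compartmental dose 3 AUCtau is wanted instead, it would need at least one or two added PK draws between Day 30 and Day 36, which is a protocol change.
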